**Metabolic Impact of Intermittent CPAP
Consent Form**

Johns Hopkins IRB # NA_00086830

Document Date: 06/23/2021

NCT02824263

Johns Hopkins Medicine - eForm A

- Use the section headings to write the eForm A, inserting the appropriate material in each. If a section is not applicable, leave heading in and insert N/A.
- When submitting eForm A (new or revised), enter the date submitted to the field at the top of eForm A.

1. Abstract

- a. Provide no more than a one page research abstract briefly stating the problem, the research hypothesis, and the importance of the research.

Obstructive sleep apnea (OSA) causes repetitive airway closure during sleep, and is associated with metabolic and cardiovascular dysfunction. The manner in which OSA affects metabolism during sleep is not well studied, but could reveal mechanisms by which OSA promotes cardiovascular diseases. We have previously shown that OSA increases free fatty acids (FFA) in subjects with congestive heart failure (CHF)[1]. Excessive plasma FFA, even when transiently elevated, can induce metabolic and vascular dysfunction[2]. Hence, nocturnal FFA elevations could be responsible for the cardio-metabolic consequences of OSA.

In this study, we will examine if OSA increases FFA in healthy (non-CHF) subjects, and the effects of treating OSA with continuous positive airway pressure (CPAP). We will also determine whether changes in nocturnal FFA caused by OSA are associated with adverse vascular endothelial function and altered glucose metabolism. This pilot study is needed before determining whether FFA levels in OSA constitute a biomarker of cardio-metabolic risk.

2. Objectives (include all primary and secondary objectives)

Specific Aim 1: To examine whether OSA, elicited by CPAP withdrawal, causes lipolysis and cardio-metabolic dysfunction.

We hypothesize that OSA activates lipolysis during sleep, resulting in high levels of plasma glycerol and FFA, which are lowered by CPAP. We also hypothesize that CPAP withdrawal will impair glucose tolerance and endothelial function, and increase glucose production during sleep.

Specific Aim 2: To examine factors associated with lipolysis during sleep.

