Sequence and Timing of visits: Each subject will undergo up 2 visits to the lab. One sleep study will be conducted while wearing CPAP for the entire night. The second sleep study will be conducted using nasal dilator strips (NDS) as a placebo, instead of wearing CPAP, the entire night. NDS have been used in other studies as a CPAP placebo and have no impact on OSA severity [6]. The studies will be performed in random order, occurring >1 week apart and no longer than 3 months apart. To maximize chances of eliciting OSA during the non-CPAP study night, patients will be asked to refrain from CPAP use, for two nights preceding their non-CPAP study night. They will be provided with ClearPassage® NDS to use at home during CPAP withdrawal nights. This will ensure CPAP “washout” since therapeutic carryover effects of CPAP have been observed in some studies[7]. Patients who were previously enrolled in the single-night study (within-night CPAP withdrawal) will be invited to return for these additional sleep studies.

Study eligibility: To be enrolled in the study, participants will need to undergo a screening questionnaire and meet inclusion/exclusion criteria. They will need to provide written consent for participation. To avoid issues of CPAP intolerance, participants must also be accustomed to using CPAP, and report that they are capable of sleeping with CPAP on.

As of March 16, 2020 (or approval of this eFormA update), and in order to mitigate risks related to COVID-19 exposure to participants and study team, phone screening procedures will be completed from the study team members' home using a connecting service, such as Google Voice or Skype Voice-to-IP to protect study team members' personal contact information while allowing them to continue job functions from a safe location. Participants will be notified of the change in procedure.

Consent: In order to minimize the need for research-only in-person visits, telemedicine visits may be substituted for in person clinical trial visits or portions of clinical trial visits where determined to be appropriate and where determined by the investigator not to increase the participants' risks. Prior to initiating telemedicine for study visits

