Following centrifugation, plasma will be transferred to cryovials for storage. The final morning sample at time of awakening (6:30 AM) will be 12 cc (3 tubes) since we plan additional assays with this sample (lipid panel, inflammatory markers) and 4 cc will be retained as whole blood for future potential analysis. In patients that have signed the optional consent for isolation of genetic material, we will collect an additional 16 cc (4 tubes) at 6:30 AM since this volume is required for isolation of peripheral mononuclear cells. In total, the blood collected will be approximately 174 cc. For patients that consent to isolation of genetic material, the total will be 190 cc. This quantity is much less than during a blood donation. Samples will be frozen at -80°C for research pertaining to metabolic effects of OSA, with the consent of participants. A morning urine sample will be collected for measurement of catecholamines.

Morning procedures:

The PSG montage will be disconnected. One IV is removed, leaving the other IV in place for use during later glucose tolerance test. Then peripheral artery tonometry, DEXA scanning, and OGTT will be performed as follows:

Peripheral arterial tonometry (EndoPAT). The subject will be in the supine position. A blood pressure cuff is placed on the non-dominant arm while the contralateral arm is used for control comparisons. Baseline measurements will be taken for 5 minutes, during 5-min occlusion of the brachial artery by inflation of the automated cuff 50 mmHg above systolic blood pressure, and for 5 minutes upon release of the cuff. Endothelium-mediated vasodilation is assessed using a finger pulse wave amplifier. The reactive hyperemia index (RHI) and the augmentation index (AI) will be derived by software and used as metrics of endothelial function and arterial stiffness respectively.

Oral glucose tolerance test (OGTT). From the indwelling antecubital IV, baseline insulin (gold top tube, 4 cc) and glucose (grey top tube, 4 cc) will be obtained. The patient will be given a 75 g glucose solution to drink within 5

minutes. Blood samples of insulin and glucose are then collected at 30, 60, 90, and 120 minutes after drinking the glucose solution. They will be asked, if possible, to remain awake during the OGTT.

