The primary outcomes is nocturnal plasma FFA levels. The main independent variable is OSA versus CPAP exposure during sleep. Since FFA are measured multiple times per subject per night, we will perform mixed linear model analysis using condition as a fixed factor and subject ID as a random factor. Sleep physiology that is measured on a continuous basis will be condensed into 30 minute bins to create a parallel data structure with metabolic parameters. As a secondary analysis, we will also examine whether there are patient-specific (“static”) determinants of FFA level during sleep such as age, sex, or body mass index and whether these variables interact with sleep (“dynamic”) variables such as OSA severity. We hypothesize that OSA exposure increases FFA, compared to CPAP. We will then examine whether sleep physiology (e.g. AHI, arousals, heart rate) is dynamically associated with FFA, and whether urine catecholamine levels are associated with increases in FFA. For variables measured once (RHI, morning lipid profile) or averaged (e.g. nocturnal FFA level) we will perform one-way ANOVA for comparisons. We will also compare sleep physiology between the 3 nights, examining variables such as apnea hypopnea index, metrics of hypoxia, and sleep architecture/duration. Data analysis will be performed with a biostatistician and described under the “Study Statistics” section.

b. Study duration and number of study visits required of research participants.

Each study subject will make two overnight visits to the sleep lab. Subjects will be screened with an initial telephone interview. During this screening, only information necessary to assess eligibility for the study will be collected, or information voluntarily provided by the patient to initiate or maintain correspondence. Subjects without any of the self-reported exclusionary criteria will be scheduled for a face-to-face visit for further screening. At this visit, eligibility for

participation in the study protocols will be confirmed. Urine screening for pregnancy in women of child-bearing age will also be performed.

c. Blinding, including justification for blinding or not blinding the trial, if applicable.

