We will include adults of all races ≥ 20 and ≤ 75 years old, with a history of mild to severe OSA (AHI or RDI > 10). They must also own a CPAP machine and report the ability to tolerate sleeping with or without CPAP during the night.

Exclusion Criteria:

1. Uncontrolled hypertension with systolic blood pressure > 170 or diastolic blood pressure > 110
2. Congestive heart failure
3. Use of, clonidine, or nicotinic acid medication
4. Diabetes requiring the use of insulin
5. Pregnancy, by urine testing in women of child-bearing age

6. Patients with a prior history of falling asleep while driving, involved in a near-miss or motor vehicle accident, or and those in high-risk occupations such as commercial drivers or pilots.
7. Hemoglobin < 10 g/dL on point of care screening.

6. Drugs/ Substances/ Devices

- a. The rationale for choosing the drug and dose or for choosing the device to be used.

During CPAP withdrawal nights (both at home and in the lab) we will use NDS as a CPAP placebo. NDS may improve snoring but have no treatment value for OSA[6]. By including NDS as a placebo, we will avoid potential confounding such as anxiety caused by stopping CPAP.

- b. Justification and safety information if non-FDA approved drugs without an IND will be administered.
N/A

Study Statistics

The overall analysis plan has been presented in section 4, “Data Analysis and Anticipated Outcomes”. In this section we briefly address the statistical methods to be used for analysis separated by specific aim:

Specific Aim 1: To examine whether OSA, elicited by CPAP withdrawal, causes lipolysis and cardio-metabolic dysfunction.

Primary outcome: FFA level, comparing between CPAP and OSA nights, analyzed using linear mixed effect models.
Independent variable: CPAP/OSA exposure.

Specific Aim 2: To examine factors associated with lipolysis during sleep.

Primary outcome: FFA level

Independent variables: OSA severity (AHI, arousal index, heart rate, urine catecholamines), Patient factors (age, sex, body mass index/fat distribution).

These analyses are primarily designed to understand the heterogeneity of lipolysis during CPAP withdrawal.

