Study-related assessments will not be charged to the subject. Parking fees will be paid. Subjects will be responsible for any treatment of conditions that are uncovered as part of the study evaluations or if they are injured as a result of being in the study.

8. Benefits

a. Description of the probable benefits for the participant and for society.

There are no direct benefits to participants for being in this study. This study will help researchers learn whether OSA causes nocturnal FFA elevations and whether CPAP is effective in preventing the elevations.

9. Payment and Remuneration

a. Detail compensation for participants including possible total compensation, proposed bonus, and any proposed reductions or penalties for not completing the protocol.

Participants will be paid up to \$600 for completing all parts of this study, based on the following procedures:

- \$200 for each sleep study (2 visits)
- \$25 for each oral glucose tolerance test and EndoPAT test (done after each of the 2 visits)
- \$50 for a DEXA scan (only done once)
- \$100 study completion bonus for participants who are able to keep their appointments as originally scheduled. They will forfeit this bonus if they must reschedule their visit(s).
- They will also receive parking reimbursement so there is no fee to come to our laboratory.

10. Costs

a. Detail costs of study procedure(s) or drug (s) or substance(s) to participants and identify who will pay for them.

Participants will not be billed for study procedures. Polysomnograms and blood tests will be billed to the study at standard CRU rates

Reference List

1. Jun, J.C., et al., *Effects of sleep apnea on nocturnal free fatty acids in subjects with heart failure*. *Sleep*, 2011. **34**(9): p. 1207-1213.
2. Schaffer, J.E., *Lipotoxicity: when tissues overeat*. *Curr.Opin.Lipidol.*, 2003. **14**(3): p. 281-287.
3. Young, T., et al., *The occurrence of sleep-disordered breathing among middle-aged adults*. *N Engl J Med*, 1993. **328**(17): p. 1230-1235.
4. Jun, J. and V.Y. Polotsky, *Metabolic consequences of sleep-disordered breathing*. *ILAR J*, 2009. **50**(3): p. 289-306.
5. Punjabi, N.M., et al., *Sleep-disordered breathing and mortality: a prospective cohort study*. *PLoS Med*, 2009. **6**(8): p. e1000132.
6. Amaro, A.C., et al., *The use of nasal dilator strips as a placebo for trials evaluating continuous positive airway pressure*. *Clinics (Sao Paulo)*, 2012. **67**(5): p. 469-74.

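### One-way ANOVA for RHI, morning lipids and night-averaged FFA ignores that each subject is measured on both nights, so real secondary effects may be missed

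*Combined protocol and SAP*

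**What the plan says.** Section 4a (Sequence and Timing of visits) describes one CPAP night and one nasal dilator strip (NDS) night per subject: "The studies will be performed in random order, occurring >1 week apart and no longer than 3 months apart". Section 4b confirms the number: "Each study subject will make two overnight visits to the sleep lab".

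The outcomes at issue are recorded once per night, and so twice per subject:

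- RHI comes from EndoPAT. Section 9 lists payment for each "oral glucose tolerance test and EndoPAT test (done after each of the 2 visits").
- The lipid panel comes from the last overnight draw: "The final morning sample at time of awakening (6:30 AM) will be 12 cc (3 tubes) since we plan additional assays".
- Night-averaged FFA is a summary of each night's serial samples.

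For these the analysis paragraph of section 4a states: "For variables measured once (RHI, morning lipid profile) or averaged (e.g. nocturnal FFA level) we will perform one-way ANOVA for comparisons". The same paragraph gives serial FFA a mixed model with a random subject factor, on the ground that FFA is sampled repeatedly within a night. Study Statistics, Aim 1, repeats this for the primary outcome only: "FFA level, comparing between CPAP and OSA nights, analyzed using linear mixed effect models". The rest of that section has an unpaired t-test between the sexes, models with FFA as the outcome, a responder comparison, regressions relating the FFA profile to morning outcomes, and exploratory gene expression. None of these compares RHI or lipids between conditions within subjects.

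**The concern.** One-way ANOVA treats the CPAP values and the NDS values as two independent groups. Here both sets come from the same people, so the assumption is false. If a person's two values are positively correlated, the true variance of the mean difference is smaller than the ANOVA assumes. Standard errors and intervals are then too wide, and a real effect can be reported as absent.

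This touches a stated hypothesis of Aim 1: "We also hypothesize that CPAP withdrawal will impair glucose tolerance and endothelial function, and increase glucose production during sleep". Of the three elements in that sentence, only endothelial function, through RHI, is explicitly tied to the ANOVA. Glucose tolerance and glucose production are not named there and have no condition-comparison method of their own. For averaged FFA, an unpaired test could also appear to contradict the primary mixed model, and the plan does not say how the two analyses rank.

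**Working it through.** **Inputs.** From the Sample Size paragraph: 78 evaluable subjects, significance level 0.05, 80% power, 15% loss, 92 enrolled. The within-person correlation ρ between nights is not in the documents and is assumed over a range. Equal SD on both nights is also assumed, and effects are in units of that SD.

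**The plan's own figure.** d = (0.047 − 0.021)/0.04 = 0.65. A two-sided two-sample t-test at 5% and 80% power needs 38.14 per group, rounded up to 39, which gives 78. Then 78/(1 − 0.15) = 91.8, rounded up to 92. Both stated figures reproduce. They were set for a sex difference in ΔFFA; the plan states no power for the ANOVA comparisons.

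**Formulas for N pairs.**

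- SE used by the ANOVA: √(2/N) = √(2/78) = 0.160 SD.
- True SE of the mean difference: √(2(1 − ρ)/N).
- SE ratio: 1/√(1 − ρ).
- Effect with 80% paired power: d = (1.96 + 0.8416)·√(2(1 − ρ)/78).
- ANOVA power at that d: Φ((d/√(2/78) − 1.96)/√(1 − ρ)).
- Effect detectable with 80% power by ANOVA: (1.96 + 0.8416·√(1 − ρ))·√(2/78).
- Pairs the ANOVA needs for 80% power at d: 2·((1.96 + 0.8416·√(1 − ρ))/d)².
- Actual type I error of the ANOVA: 2Φ(−1.96/√(1 − ρ)).

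| ρ (assumed) | SE ratio | 80%-power effect, paired (SD) | 80%-power effect, ANOVA (SD) | ANOVA power where paired has 80% | Pairs needed by ANOVA | Actual type I error |
|---|---|---|---|---|---|---|
| 0 | 1.00 | 0.45 | 0.45 | 80% | 78 | 5% |
| 0.1 | 1.05 | 0.43 | 0.44 | 77% | 85 | 3.9% |
| 0.3 | 1.20 | 0.38 | 0.43 | 68% | 101 | 1.9% |
| 0.5 | 1.41 | 0.32 | 0.41 | 51% | 130 | 0.6% |
| 0.7 | 1.83 | 0.25 | 0.39 | 22% | 195 | about 0.03% |
| 0.8 | 2.24 | 0.20 | 0.37 | 6% | 272 | about 0% |

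Worked line for ρ = 0.5: d = 2.8016 × √(1/78) = 0.317. ANOVA power = Φ((0.317/0.160 − 1.96)/0.707) = Φ(0.03) = 51%.

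**Simulation check.** With 100,000 trials per value of ρ, t critical values and the effect set to 80% paired power, ANOVA power was 69%, 52%, 23% and 7% at ρ = 0.3, 0.5, 0.7 and 0.8.

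**The same loss at a fixed effect.** For a true shift of 0.3 SD (assumed) and 78 pairs, ANOVA power is 45%, 44% and 43% at ρ = 0.3, 0.5 and 0.7. Paired power is 60%, 74% and 92%.

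**Averaged FFA, indicative only.** The preliminary figures give a mean Δ of (13 × 0.047 + 7 × 0.021)/20 = 0.038 mmol/l, with SD of Δ 0.04. A paired analysis of 78 subjects has over 99% power. If the between-subject SD were 0.10 or 0.15 mmol/l (assumed), then ρ = 1 − 0.04²/(2·SD²) is 0.92 or 0.96, and ANOVA power is about 92% or 2%. The preliminary Δ may come from the earlier single-night study.

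**The case against.** The strongest reply is that one-way only counts factors, and a repeated-measures ANOVA on condition is also one-way. The authors use random subject effects elsewhere and express FFA as a within-person change, so they may have meant a repeated-measures test. That is possible, but the text does not say it. The paragraph uses a subject term when there are several samples per night and drops it when there is one value per night. Even on the kind reading, the wording has to change for the analysis to be reproducible.

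A second reply concerns size. The fall from 68% to 6% arises partly because the effect is reset at each correlation to the one with 80% paired power. At a fixed 0.3 SD, ANOVA power is nearly flat and it is the paired power that rises. An effect of 0.5 SD would have about 92% to 99% ANOVA power over correlations of 0.3 to 0.8. The plan sets no effect or power target for RHI or lipids. All this stands: the loss is real for any positive correlation, but its size is unknown and matters most for modest effects.

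Third, the trial calls itself a pilot, these outcomes are secondary, the error is conservative, and averaged FFA is backed by the primary mixed model. These points limit the severity. They do not make the test right.

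**Conclusion.** The concern holds. As written, the plan applies an unpaired test to paired data for RHI, morning lipids and night-averaged FFA, and no other part of it supplies a paired comparison between conditions for RHI or lipids. At 78 pairs the ANOVA standard error is 1.20 to 2.24 times too large for correlations of 0.3 to 0.8. From 0.3 upward, matching the paired analysis would take 101 or more pairs, above the 92 to be enrolled. These figures rest on assumed correlations and equal SDs on the two nights. The primary FFA comparison is untouched, false positives are not inflated, and the sample size is not in dispute. This should be fixed before analysis, chiefly because RHI carries the endothelial hypothesis of Aim 1.

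**What to change.** In section 4a, replace the one-way ANOVA with a linear mixed model that has condition and period as fixed effects and subject as a random effect, for RHI, morning lipids and night-averaged FFA. Use the same model for the other once-per-night condition comparisons: augmentation index, OGTT summaries and whole-night sleep measures. A paired t-test or Wilcoxon signed-rank test is a simpler alternative that keeps the pairing but does not adjust for period. State that the mixed model on serial FFA is the primary FFA analysis and that averaged FFA is supportive.

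In the same edit, reconcile "We will also compare sleep physiology between the 3 nights" with the two-visit design. It looks like stale text. If so, it should refer to the two lab nights. If it is meant to include the earlier night of participants returning from the single-night study, the plan should say so. The main point does not depend on this.

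The cost is wording only. No new data, visits or subjects are needed. The period term uses the night order already set by randomization and costs one degree of freedom.

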To prevent CPAP “carry-over” effects, preceding the non-CPAP night, participants will be requested to abstain from CPAP use for 2 nights, if possible. If they have historically been unable to discontinue CPAP for this length of time, they may continue CPAP until the in-lab study. For CPAP withdrawal nights, NDS will be used as a placebo. This will control for unintended effects of stopping CPAP such as anxiety before sleep. Lab assays will be performed by a technician blinded to the CPAP status of participants.

d. Justification of why participants will not receive routine care or will have current therapy stopped.

This study is being conducted to examine the effects of OSA and its treatment on lipid metabolism. The rapid kinetics of FFA turnover requires careful attention to dynamic changes in plasma FFA during sleep with or without CPAP. Studying patients with known OSA, adherent to CPAP therapy, has several advantages. First, CPAP-naïve patients may not tolerate CPAP, and experience paradoxically increased sleep loss, stress, and sympathetic stimulation of lipolysis. Second, we will greatly reduce time and resource costs needed to identify undiagnosed subjects with OSA. Third, CPAP withdrawal has been utilized in other studies, yielding highly reproducible physiological effects of OSA[8]. Finally, intermittent/inconsistent CPAP use is common in clinical practice, and the metabolic consequences are not known. After CPAP withdrawal (total of 3 nights), patients may resume their routine CPAP use.

e. Justification for inclusion of a placebo or non-treatment group.

In terms of NDS as a CPAP placebo during withdrawal nights, we wish to minimize confounding that might be introduced by other factors such as anxiety about stopping CPAP. Participants will be told that NDS are not as effective as CPAP for treatment of OSA. The written consent will state that NDS may be effective for nasal congestion but that long-term data have not shown an effect on OSA severity.

f. Definition of treatment failure or participant removal criteria.

If participants cannot tolerate CPAP off, they will be removed from the study.

g. Description of what happens to participants receiving therapy when study ends or if a participant’s participation in the study ends prematurely.

Following the non-CPAP night, subjects may resume routine CPAP use.

5. Inclusion/Exclusion Criteria

Inclusion Criteria:

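### Sections 4c and 6a credit the nasal strips with removing confounding by anxiety about stopping CPAP; in unblinded participants told the strips are inferior, they can at most reduce it

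*Combined protocol and SAP*

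**What the plan says.** The plan describes the strips' purpose in three places, with different strength.

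- Section 4c (blinding): "This will control for unintended effects of stopping CPAP such as anxiety before sleep".
- Section 6a (device rationale): "By including NDS as a placebo, we will avoid potential confounding such as anxiety caused by stopping CPAP".
- Section 4e (placebo justification): "we wish to minimize confounding that might be introduced by other factors such as anxiety about stopping CPAP".

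Section 4e then sets out the disclosure: "Participants will be told that NDS are not as effective as CPAP for treatment of OSA". The written consent will add that the strips may help a congested nose but that "long-term data have not shown an effect on OSA severity". The only blinding described is in 4c: "Lab assays will be performed by a technician blinded to the CPAP status of participants".

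For the primary outcome, the Data Analysis section says "we will perform mixed linear model analysis using condition as a fixed factor and subject ID as a random factor". Aim 1 in Study Statistics compares FFA between the CPAP and OSA nights and interprets the difference as lipolysis caused by OSA. No measure of anxiety or expectation is listed for either visit.

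**The concern.** The plan itself names anxiety about stopping CPAP as a possible confounder and relies on the strips to deal with it. Participants own a CPAP machine, are used to it, and wear strips only when CPAP is off. They know which condition they are in and have been told it is the weaker one. A substitute presented in that way may reassure, but it cannot be assumed to take away worry about losing the treatment it replaces.

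What is at stake is the interpretation of Aim 1. If anxiety on the strip night raised FFA, the effect would lie in the hypothesised direction and would be counted as part of the OSA effect. A reader who took 4c and 6a at face value would think that this explanation had been excluded by design.

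**Working it through.** **1. The three statements against the disclosure.** *Control for* (4c) and *avoid* (6a) both say that the confounder is dealt with. *Minimize* (4e) says that it is made smaller. Being told that the strips are inferior, with no demonstrated effect on OSA severity, is compatible with *minimize*. It does not support the other two.

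**2. Does another design feature remove it?**

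- *Random order* balances period effects. Anxiety about stopping CPAP goes with the condition, whichever visit comes first, so order does not balance it.
- *Blinded assays* protect the measurement of FFA, not the participant's state during the night.
- *The primary model* has condition as its fixed factor and no term that could separate anxiety from OSA.
- *Heart rate and urine catecholamines* cannot separate them either, because the plan treats both as markers of sympathetic activation by OSA (Objectives, Aim 2).
- *Awake blood samples* start at 17:30, about five hours before the sleep study, but no between-night comparison of them is specified.

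**3. Size: the available inputs.** The Sample Size section gives a preliminary FFA change of 0.047 ± 0.04 mmol/l in 13 men and 0.021 ± 0.04 in 7 women.

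- The plan's own figures reproduce: d = (0.047 − 0.021)/0.04 = 0.65. The two-sided t-test at 0.05 and 80% power needs 38.14 per group, so 39 per group and 78 in all; 78/0.85 = 91.8, so 92 enrolled. The present point changes none of these.
- Mean preliminary rise, weighted by n: (13 × 0.047 + 7 × 0.021)/20 = 0.758/20 = 0.0379 mmol/l. Weighting the sexes equally: (0.047 + 0.021)/2 = 0.034 mmol/l.

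**4. Illustration of sensitivity (assumptions, not estimates).** Take 0.04 as the SD of the within-person difference between nights, N = 78, a normal approximation with one difference per person, and no true OSA effect. Then SE = 0.04/√78 = 0.00453. For an anxiety effect b on the strip night, the chance of a significant result is 1 − Φ(1.96 − b/SE) + Φ(−1.96 − b/SE).

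| Assumed b (mmol/l) | Share of 0.0379 | Chance of a significant contrast |
|---|---|---|
| 0 | 0% | 5% |
| 0.002 | 5% | 7% |
| 0.005 | 13% | 20% |
| 0.010 | 26% | 60% |
| 0.0127 | about one third | 80% |
| 0.020 | 53% | 99% |

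The table shows how sensitive a contrast of this precision would be to such an effect. It does not show that the effect exists.

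**5. The sex comparison.** If anxiety adds the same amount a in men and women, the difference is (men + a) − (women + a), and a cancels. Only an anxiety effect that differs by sex would bias the comparison that sets the sample size.

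**The case against.** The case on the other side is substantial.

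- *The strips may help.* The message to participants is comparative, and a partly reassuring substitute can lower worry. This stands. A reader might infer that the strips do nothing for anxiety; the documents do not support that.
- *There are safeguards.* Participants must report that they can sleep without CPAP, and those who cannot tolerate being off it are removed (4f). Two home nights with strips normally come before the laboratory night. These features probably limit acute anxiety, but they do not exclude ordinary worry. Section 4c also lets people who have been unable to stop for two nights stay on CPAP until the laboratory study.
- *The link from stress to FFA is an inference.* Section 4d says CPAP-naïve patients may not tolerate CPAP and may "experience paradoxically increased sleep loss, stress, and sympathetic stimulation of lipolysis". A reader might take this as the protocol saying that anxiety off CPAP drives lipolysis in the trial's participants. It does not: it concerns a different group and lists stress beside sympathetic stimulation. The route is plausible, no more.
- *The issue is not wholly uncheckable.* Awake FFA could be compared between nights, and the Aim 2 analyses relating FFA to AHI or ODI within the night, with time lags, are more specific to OSA than the contrast between nights. Both points stand, although the first is not planned and the second does not alter how Aim 1 is read.
- *No report has yet cited the strips as excluding anxiety.* True. Aim 1 openly names CPAP withdrawal as the means of eliciting OSA, and the outcome is an objective, blinded assay. But 4c and 6a would license that citation.

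**Conclusion.** The point holds in limited form. The wording of 4c and 6a claims more than the design delivers; that of 4e does not. Residual anxiety is tied to the off-CPAP condition, is not balanced by order, and could contribute to the Aim 1 contrast to the extent that it occurs and raises FFA. Its size is unknown, and zero is possible.

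A reader might infer that 13% to 26% of the reported OSA effect would be due to stress. That range only restates an assumed 0.005 to 0.010 mmol/l, and nothing in the documents supports those values. The chances in the table rest further on the assumed SD and on treating the analysis as a simple paired comparison.

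The sample size is unaffected. The point concerns what the trial may conclude, and it is worth settling because the remedy is cheap.

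**What to change.** 1. Reword 4c and 6a to match *minimize* in 4e, and state that participants are unblinded to condition while FFA assays are blinded.
2. Record a one-item anxiety rating at bedtime on both nights and report it by condition.
3. Prespecify a between-night comparison of the awake, pre-sleep FFA samples already drawn from 17:30. State its limits: two preceding nights off CPAP may also shift these values, and a pre-sleep sample does not capture anxiety that persists overnight.
4. Describe the primary contrast as the effect of CPAP withdrawal, and do not cite the strips as excluding anxiety.
5. If a model with the within-person change in the rating as a covariate is fitted, label it exploratory. The rating is taken after the condition is known and may itself be a consequence of withdrawal, so adjusting for it does not isolate an OSA effect.
6. Keep the disclosure to participants as it is.

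The cost is protocol wording, about one minute per visit, and two simple tabulations. The downside is a more modest causal claim for Aim 1.
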